9.2.4 Reporting of Pregnancy

If a subject becomes pregnant during the study, she must be instructed to stop taking the study drug and immediately inform the Investigator. The Investigator must report all pregnancies within **24 hours** to the Sponsor as per Section 9.2 Reporting Procedures, regardless of seriousness. The Investigator should counsel the subject and discuss the risks of continuing with the pregnancy and the possible effects on the fetus. Monitoring of the subject should continue until conclusion of the pregnancy. The clinical outcome of the pregnancy should be documented. Specifically, the estimated date of conception, expected date of delivery, actual date of delivery, date of last

Compound No.: GTx-024 Author: [name]

menstrual period, and details of contraceptives should be documented. The pregnancy course should be described in full. If the subject gives birth, the weight and length of the child, Apgar scores (with explanation of score < 10), and congenital abnormalities should be documented. Concomitant drugs and medical history of the mother should be documented. Smoking status and alcohol intake during pregnancy and illicit drug use prior to and during pregnancy should be recorded. Pregnancy will be followed until completion. If the new-born is healthy, additional follow-up is not necessary.

9.3 Type and Duration of Follow-up of Subjects after Adverse Events

AEs will be collected up until 28 days after the last dose of study treatment, and will continue to be followed up until one of the following occurs:

- Resolved or improved to baseline
- Death
- Start of new anticancer regimen
- Investigator confirms that no further improvement can be expected

9.4 Halting Rules

If in the opinion of the Investigator, the participation in the study is or is becoming detrimental to the well-being of a particular subject, this issue should be discussed with the Medical Monitor for this study and a determination made regarding dose reduction, interruption, or withdrawal of the subject from the study.

Dose reduction, interruption, or withdrawal of the subject from the study should be considered if:

- ALT or AST > 8 × ULN
- ALT or AST > 5 × ULN for more than 2 weeks
- ALT or AST > 3 × ULN and (total bilirubin > 2 × ULN or INR > 1.5)

Compound No.: GTx-024 Author: [name]

 ALT or AST > 3 × ULN with the appearance of fatigue, nausea, vomiting, right upper quadrant pain or tenderness, fever, rash, and/or eosinophilia (> 5%)

For subjects with known liver metastasis and elevated ALT or AST of ≤ 5 × ULN at baseline, discontinuation of treatment should be considered if:

ALT or AST > 5 × ULN and total bilirubin > 2 × ULN

All subjects discontinued from dosing should be followed until abnormal values return to normal.

ALL DISCONTINUATIONS SHOULD BE DISCUSSED WITH THE MEDICAL MONITOR PRIOR TO DISCONTINUATION.

If any 2 out of the first 10 subjects enrolled in the 18 mg arm meet the above hepatotoxicity criteria, or if a total of 5 subjects ever meet these criteria in the 18 mg arm, the 18 mg dose will be reduced to 9 mg for all subjects; the 18 mg arm will be permanently halted and all subjects will be enrolled into the 9 mg arm.

If a total of 5 subjects in the 9 mg arm ever meet the above hepatotoxicity criteria, the study will be halted.

9.5 Safety Oversight

In order to protect the safety of the subjects, an SMC will be established for the study to review the safety data on an ongoing basis. The SMC will consist of, as a minimum, the Medical Monitor, a Safety Reviewer with an oncology background, a statistician, and two GTx, Inc. representatives, consistent with the SMC charter.

The Medical Monitor will be a physician with relevant expertise whose primary responsibility is to provide independent safety monitoring in a timely fashion through review of AEs, immediately after they occur or are reported, with follow-up through to resolution. The Medical Monitor will evaluate individual and cumulative participant data when making recommendations regarding the safe continuation of the study.

Compound No.: GTx-024 Author: [name]

The Medical Monitor will be selected based on relevant study-related or therapeutic expertise and participation is for the duration of the study. The Medical Monitor will be able to readily access participant records in real time.

Compound No.: GTx-024 Author: [name]

10 CLINICAL MONITORING

The purpose of the site monitoring visit is to ensure that the study is being conducted in accordance with the protocol (and any subsequent amendments), current ICH Guideline on Good Clinical Practice (GCP) requirements, and applicable IRB/IEC and regulatory requirements.

An authorized study monitor (clinical research associate [CRA]) will visit the site prior to initiation and at periodic intervals to review the study records (including ICFs, inventory of study drug, and eCRFs), and assess compliance with the study protocol. The monitor(s) will also visit at conclusion of the study to help resolve any remaining data queries and close out all record keeping.

It is the responsibility of the Investigator to make sure all necessary source documentation and records are available to the CRA during his/her visit and to provide a suitable space for the CRA to review these documents. Additionally, the Investigator must also be available as needed during the monitoring visit. It is the CRA's responsibility to arrange the visits with the unit in advance and to notify the unit of the documentation that he/she will need during the visit.

All findings resulting from monitoring visits will be documented and shared with the Investigator and Sponsor via follow-up letters and monitoring reports. As much as possible, issues/discrepancies should be resolved during the monitoring visits, but those remaining at the end of the visit will be followed through until resolution.

Compound No.: GTx-024 Author: [name]

11 STATISTICAL CONSIDERATIONS

This section is an overview of the statistical design and its rationale. A separate Statistical Analysis Plan (SAP) will provide further detail of statistical tests, handling of missing data, and various methods for imputing time-to-event to account for the difference between the last known event free time and the subsequent first event date, as well as specifications of tables, figures, and listings.

11.1 Study Hypotheses

This trial will employ a Simon's two-stage (optimal) design independently for each dose arm, 9 mg and 18 mg. The assumptions for the design are as follows:

- H₀: CBR ≤ 0.10
- H₁: CBR ≥ 0.30
- $\alpha = 0.025$ (one-sided)
- Power = 90%

11.2 Sample Size Considerations

Based on the above assumptions, a sample size of N = 44 ER+/AR+ BC subjects with centrally confirmed AR+ status who receive at least one dose of study treatment (evaluable subjects) are needed for each arm that proceeds to the second stage. An arm will proceed to the second stage if at least 3 subjects among the first 18 evaluable subjects randomized achieve CB, defined as CR, PR, or SD as per RECIST 1.1, as determined by central review. If an arm proceeds to the second stage, a statistical success that favors further evaluation of the dose arm(s) in future trials will require at least 9/44 subjects to achieve CB at week 24, i.e., the null hypothesis of an unacceptably low rate of CB, \leq 10.0%, can be rejected in favor of the alternative hypothesis that indicates the higher rate, \geq 30.0%, is more likely. The lower limit of the exact 95% confidence interval at exactly 9 CBs, 11.0%, exceeds 10.0%¹².

Compound No.: GTx-024 Author: [name]

At any time during the first stage, if 3 evaluable subjects in any one arm achieve CB at week 24, that arm will proceed to the second stage; otherwise, it will be halted for lack of efficacy. If at any time, 9 evaluable subjects in an arm achieve CB at week 24, the efficacy criteria for that arm has been met; however, the arm should proceed to full accrual of 44 evaluable subjects in the successful arm(s) in order to better characterize the CB rate, evaluate secondary endpoints, and describe the safety profile of the dose level(s). To reiterate, the intent of the trial is not to statistically compare the CB rate between the two dose arms and the trial is not powered to do so.

Subjects whose AR+ status is not centrally confirmed will be replaced in order to accrue the necessary number of evaluable AR+ subjects to be included in the primary analysis. Subjects who are not confirmed AR+ may remain on the trial, but will not be part of the primary efficacy analysis – these subjects will contribute to secondary and tertiary analyses as noted below. Subjects who are randomized but never receive study drug will be replaced as well. Assuming that 25% of subjects enrolled are not evaluable for the primary efficacy analysis for the reasons noted above, up to 30 additional subjects may need to be randomized.

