4 STUDY DESIGN

This is an open label, multicenter, multinational, randomized, parallel design Phase 2 study to assess the efficacy and safety of GTx-024 in postmenopausal subjects with ER+/AR+ BC. Subjects will be randomized to receive either GTx-024 9 mg or 18 mg given PO daily for up to 24 months. Each dose arm will be treated independently and each assessed for efficacy using Simon's two-stage (optimal) design¹. Subjects will be randomized in a 1:1 fashion to one of the two dose arms. Randomization will be stratified by subjects presenting with bone only metastases and all other subjects, and further by setting of immediately preceding therapy (adjuvant setting or metastatic setting) in order to balance the proportion of subjects with these presenting features in each dose arm. There is no intent to statistically compare the two dose arms, but to determine whether either or both doses result in an acceptable CBR, defined as the proportion of evaluable subjects (i.e., subjects with centrally confirmed AR+ and who receive at least one dose of study drug) with either CR, PR, or SD by RECIST 1.1 at week 24, consistent with 30% while maintaining an acceptable safety profile. Given such a result, future exploration of GTx-024 in ER+/AR+ BC would be warranted at that dose level.

Thirty-six to 88 (36–88) subjects with centrally confirmed AR+ who receive at least one dose of study drug (evaluable subjects) will be needed for primary efficacy analysis purposes and will be a subset of the FAS. Thirty-six to one hundred and eighteen (36–118) subjects, including replacement subjects, will be randomized in a 1:1 fashion to receive a daily PO dose of either GTx-024 9 mg or 18 mg. Thirty of the aforementioned subjects may be considered replacement subjects to account for lack of centrally confirmed AR+ status or for the rare subject who is randomized but does not receive study drug (assumes 25% of enrolled subjects are not evaluable for the primary efficacy analysis). Other statistical parameters that are part of the sample size calculation are α = 0.025 (one-sided) and power = 90%. The first stage in each study arm will be assessed among the first 18 evaluable subjects. If at least 3/18 subjects achieve CB (defined as CR, PR, or SD) at week 24, the arm will proceed to the second stage of recruitment up to a total of 44 evaluable subjects per arm. Otherwise, the arm will be discontinued for lack of efficacy. Statistical significance, i.e., rejection of

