Compound No.: GTx-024 Author: [name]

the null hypothesis of an unacceptably low CBR of \leq 10% in favor of the alternative hypothesis that indicates the higher rate, \geq 30%, is more likely, will be declared if at least 9/44 subjects achieve CB at week 24 in that arm.

Subjects who are not centrally confirmed AR+ may remain on the trial, but will not be part of the primary efficacy analysis – these subjects will contribute to secondary and tertiary analyses as noted in Section 11 Statistical Considerations.

Subjects on the 18 mg treatment arm who experience an AE with Grade ≥ 3 intensity (National Cancer Institute-Common Terminology Criteria for Adverse Events [NCI-CTCAE], Version 4.0) and/or intolerance may have a dose reduction from 18 mg to 9 mg per day or a drug interruption based on the medical judgment of the Investigator and after confirmation by the study Medical Monitor. The drug interruption may last for a period of up to 5 days after which the subject must be rechallenged with study drug (18 mg or 9 mg) or discontinued from the study. In the case of a dose reduction, once the AE has resolved or reduced in intensity to Grade 1, the subject may be rechallenged with 18 mg or maintained at 9 mg at the discretion of the Investigator.

Subjects on the 9 mg treatment arm who experience an AE with Grade ≥ 3 intensity (NCI-CTCAE 4.0) and/or intolerance may have a drug interruption based on the medical judgment of the Investigator and after confirmation by the study Medical Monitor. The drug interruption may last for a period of up to 5 days after which the subject must be rechallenged with study drug (9 mg) or discontinued from the study.

In the event of hepatotoxicity, please also refer to Section 9.4 Halting Rules.

For safety analysis, subjects will be analyzed in the treatment arm in which they are initially dosed. For efficacy analysis, subjects will be analyzed according to the treatment arm to which they were randomized.

The subjects who demonstrate CB will be treated for up to 24 months from the date of randomization (as long as they continue to demonstrate CB from the treatment during

[figure not shown]

Compound No.: GTx-024 Author: [name]

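### Reaching 9/44 is to be declared as making a CBR of 30% or more the more likely rate, but the count rule supports only a CBR above 10%

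*Combined protocol and SAP*

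**What the plan says.** Section 11.1 sets up "Simon's two-stage (optimal) design independently for each dose arm", with a null of CBR at or below 10% and an alternative of CBR at or above 30%. Section 4 gives the error rates as "α = 0.025 (one-sided) and power = 90"%. Nothing is said about a true CBR between 10% and 30%.

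Under Section 11.2 an arm continues if at least 3 of its first 18 evaluable subjects achieve clinical benefit, and it succeeds with "at least 9/44 subjects to achieve CB at week 24". The conclusion attached to success is that the null "can be rejected in favor of the alternative hypothesis that indicates the higher rate", 30% or more, as the more likely. The Summary (Statistical Considerations) says the same. Section 4 makes it the meaning of statistical significance: that the higher rate "is more likely, will be declared if at least 9/44 subjects achieve CB at week 24 in that arm".

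Section 11.4.3.2, the primary efficacy analysis, is narrower. It describes 9 as the smallest count that excludes a 10% rate, and plans an exact 95% confidence interval for the CBR.

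**The concern.** One threshold is given two meanings. Section 11.4.3.2 attaches to it what a one-sided test of 10% can deliver. The other three places add a statement about 30%. In a Simon design the alternative rate fixes the power; rejecting the null does not establish that rate. A count that just meets the rule is 9/44, or 20.5%, about midway between the two hypotheses, so the rates left out of the conclusion are those closest to the data.

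What is at stake is the statement that accompanies a positive arm. Section 11.2 says success favours further evaluation of the dose, and Section 2.2 says the data will inform the design of possible later trials. A reader who takes the declaration at face value would attach to the dose an effect size that the rule has not shown.

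**Working it through.** **Inputs.** Null rate 0.10 and alternative rate 0.30 (Section 11.1); one-sided alpha 0.025 and power 90% (Sections 4 and 11.1); at least 3/18, then at least 9/44 (Sections 4 and 11.2). A missing week 24 assessment counts as no benefit (Sections 11.4.2 and 11.4.3.7), so the denominator stays at 44. The rates of 15%, 20% and 25% are illustrative and are not in the documents.

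**1. Reproduce the design.** For a true rate p,

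P(success | p) = Σ (x = 3 to 18) Bin(x; 18, p) × P[Bin(26, p) ≥ 9 − x].

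This gives 0.0236 at p = 0.10 and 0.904 at p = 0.30. The probability of stopping after stage 1 at 10% is 0.734, so the expected size under the null is 18 + 26 × (1 − 0.734) = 24.9. A search for the smallest expected size subject to alpha ≤ 0.025 and power ≥ 0.90 returns the protocol's own rule. The design is confirmed.

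**2. Success probability between the hypotheses**, from the same formula:

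| True CBR | P(success) |
|---|---|
| 10% | 2.4% |
| 15% | 17.9% |
| 20% | 47.5% |
| 25% | 74.8% |
| 30% | 90.4% |

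**3. What the data at the threshold favour.** With x of 44, the likelihood ratio of rate a to rate b is (a/b)^x × [(1 − a)/(1 − b)]^(44 − x). The stage 1 stopping rule cancels from this ratio.

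- 30% against 10% at 9/44: 3^9 × (7/9)^35 = 2.98. At 10/44 it is 11.5.
- 20% against 30% at 9/44: (2/3)^9 × (8/7)^35 = 0.0260 × 107.1 = 2.79.
- 20% against 30% at 10/44: (2/3)^10 × (8/7)^34 = 0.01734 × 93.7 = 1.62.
- 20% against 30% at 11/44: 0.95, marginally the other way.

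The last comparison balances at x = 44 ln(8/7) / [ln(8/7) + ln(3/2)] = 10.9, so 20% is favoured over 30% at 9 and 10 only. Because 9/44 lies below 30%, 30% is the best-fitting value in the whole range of 30% or more; higher rates fit worse still.

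**4. How often a success falls at 9 or 10.** Given success, these counts make up 49% of outcomes if the true CBR is 20% (0.233/0.475) and 12% if it is 30% (0.113/0.904).

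**5. The interval at the threshold.** The Clopper-Pearson 95% interval at 9/44 is 9.8% to 35.3%. It contains 30%, but also 15%, 20% and 25%. Section 11.2 quotes a lower limit of 11.0%, citing a different exact method; two other exact intervals tried gave about 10.8%. The choice does not affect this point, since the upper limits, from 34.9% to 35.3%, all leave the same middle rates inside.

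**The case against.** The strongest reply is that the sentence is comparative. Section 11.1 states two hypotheses, and between them 30% is favoured at 9/44 by 2.98 to 1. That stands: on this reading the wording is true. A reader might infer that it is simply false, and the documents do not support that. But the sentence does not say it is confined to those two rates, and Section 4 has it declared as the meaning of significance.

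It can also be said that the right reading is already in Section 11.4.3.2, that Section 11.2 justifies the threshold only by a lower limit above 10%, that the primary objective is estimation, and that exact intervals are planned. All of this is correct. It limits the harm and supplies the replacement wording, but leaves three sections saying more than the fourth.

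The gap between the two rates is inherent in a Simon design. That is so, and the design is not in question.

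Three stronger readings should be set aside:

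- Section 4's aim of a CBR "consistent with 30% while maintaining an acceptable safety profile" might be taken as the same error. It states a goal, and at 9/44 the interval includes 30%.
- A later trial might be said to be underpowered because it would be planned on 30%. No such trial is sized in the documents, so this is speculation.
- The preference for 20% over 30% might be extended to every successful arm. It holds at 9 and 10 of 44 only.

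**Conclusion.** The concern holds as a matter of the stated conclusion, not of the test. Sample size, cut-offs and error rates are right. Meeting 9/44 supports a CBR above 10%. The claim that 30% or more is more likely holds only against 10% or less. It leaves out the middle rates, of which 20% is favoured over 30% by 2.79 at 9/44 and 1.62 at 10/44, and an arm with a true CBR of 20% would be declared successful almost half the time.

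The success probabilities assume independent subjects with a common rate and the rule applied exactly as written. The choice of 20% is illustrative, but the conclusion does not hang on it: from 15% to 25% the chance of success runs from 17.9% to 74.8%. This is a wording correction worth making because the sentence is to be declared as the trial's result.

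**What to change.** In the Summary (Statistical Considerations), Section 4 and Section 11.2, replace the conclusion about the higher rate with the one that Section 11.4.3.2 already supports, for example: *At least 9/44 clinical benefits rules out a CBR of 10% or less; it does not by itself show a CBR of 30% or more.* Add one line to Section 11.2 giving the probability of success at true CBRs of 15%, 20% and 25% (17.9%, 47.5%, 74.8%). State that any claim of consistency with 30% will rest on the estimated CBR and its planned exact 95% interval. The aim stated in Section 4 can stay.

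The cost is a few sentences and a less favourable claim for a positive arm. Sample size, thresholds, the go/no-go rule and conduct do not change.

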Description of Agent or Intervention:	Three (3) GTx-024 3.0 mg softgels for a 9 mg daily dose or six (6) GTx-024 3.0 mg softgels for an 18 mg daily dose will be taken PO with water at approximately the same time each day, with or without food.		
Estimated Time to Complete Enrolment:	It is anticipated the time to complete enrollment will be 12 months.		
Statistical Considerations	This trial will employ a Simon's two-stage (optimal) design independently for each dose arm, 9 mg and 18 mg. The assumptions for the design are as follows: • H₀: CBR ≤ 0.10 • H₁: CBR ≥ 0.30 • Alpha (α) = 0.025 (one-sided) • Power = 90%. Based on the above assumptions, a sample size of N = 44 centrally confirmed AR+ subjects who have received at least one dose of study medication (evaluable subjects) are needed for each arm to proceed to completion of the second stage. An arm will proceed to the second stage if at least 3 subjects among the first 18 evaluable subjects randomized in stage 1 achieve CB, defined as CR, PR, or SD, as per RECIST 1.1 as determined by central review. Otherwise, the arm will be closed due to lack of efficacy. If an arm proceeds to the second stage, the efficacy criteria favoring further evaluation of the dose arm(s) in future trials will require at least 9/44 subjects to achieve CB; i.e., the null hypothesis of		
	an unacceptably low rate of CB, ≤ 10.0%, can be rejected in favor of the alternative hypothesis that indicates the higher rate, ≥ 30%, is more likely.		

Compound No.: GTx-024 Author: [name]

Over-enrollment: Subjects who are not centrally confirmed AR+ will be replaced by an over-enrollee in order to accrue the 44 subjects of the evaluable subset of the FAS. Subjects who are randomized but not centrally confirmed AR+ may, at the discretion of the Investigator, be maintained on the study, but these subjects will not be part of the evaluable subset of the FAS used for the primary analysis. However, these subjects are part of the FAS and will contribute to analysis as specified in Section 11 Statistical Considerations. Subjects who are randomized but do not receive treatment will also be replaced by an over-enrollee. Subjects who do not receive any study medication will not be included in any efficacy analyses. These two conditions may result in up to an additional 30 subjects being randomized (assumes 25% of enrolled subjects are not evaluable for the primary efficacy analysis).

Compound No.: GTx-024
Author: [name]

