5 STUDY ENROLLMENT AND WITHDRAWAL

5.1 Subject Inclusion Criteria

Subjects eligible for inclusion in this study must meet **all** of the following criteria:

- Adult women (≥ 18 years of age) with metastatic or recurrent locally advanced BC, not amenable to curative treatment by surgery or radiotherapy, with objective evidence of disease progression.
 - Women must have received ≥ 1 prior hormonal treatment(s) in the metastatic or adjuvant setting
 - If the most recent hormonal treatment was in the metastatic setting, duration of response (tumor regression or stabilization of disease) to this specific course of therapy must be ≥ 6 months
 - If the most recent hormonal treatment was in the adjuvant setting, duration of response (disease free) to this specific course of therapy must be ≥ 3 years
- Histological or cytological confirmation of ER+ BC as assessed by a local laboratory using slides, paraffin blocks, or paraffin sample or by medical history: ER+ (confirmed as ER expression more than or equal to 1% positive tumor nuclei)
- 3. Human epidermal growth factor receptor 2 (HER2)-negative tumor by local laboratory testing (immunohistochemistry [IHC] 0, 1+ regardless of fluorescence in situ hybridization [FISH] ratio; IHC 2+ with FISH ratio lower than 2.0 or HER2 gene copy less than 6.0; FISH ratio of 0, indicating gene deletion, when positive and negative in situ hybridization [ISH] controls are present)
- 4. Availability of paraffin embedded or formalin fixed tumor tissue; OR, a minimum of 10 and up to 20 slides of archived tumor tissue for central laboratory confirmation of AR status and molecular subtyping. Metastatic tumor tissue is preferred when possible
- 5. Postmenopausal women. Postmenopausal status is defined by the National Comprehensive Cancer Network as either:

Compound No.: GTx-024 Author: [name]

- Age ≥ 55 years and one year or more of amenorrhea
- Age < 55 years and one year or more of amenorrhea, with an estradiol assay
 20 pg/mL
- Age < 55 years and surgical menopause with bilateral oophorectomy
 - a. *Note:* Ovarian radiation or treatment with a luteinizing hormonereleasing hormone (LH-RH) agonist (goserelin acetate or leuprolide acetate) is not permitted for induction of ovarian suppression
- 6. Radiological or clinical evidence (bone scan, computerized tomography [CT], and magnetic resonance Imaging [MRI]) of recurrence or progression within 30 days before randomization

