11.4 Final Analysis Plan

11.4.1 Analysis sets

Full Analysis set (FAS): All subjects who are randomized and receive at least one dose of study drug.

Evaluable subjects: Subjects in the FAS who have centrally confirmed AR+ status; these subjects are the subjects in the primary efficacy analysis.

Compound No.: GTx-024 Author: [name]

Per protocol set (PPS): All subjects with centrally confirmed AR+ who have baseline scans, receive at least 80% of the anticipated doses, and complete the week 24 RECIST 1.1 evaluation, and have no major protocol deviations.

Safety analysis set (SAS): All subjects who are randomized and receive at least one dose of study drug.

Safety analysis subjects will be analyzed in the treatment arm in which they are initially dosed. Efficacy analysis subjects will be analyzed according to the treatment arm to which they were randomized.

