11.4.3.2 Primary efficacy analysis

The primary efficacy analysis is based on rules as set forth in Simon's two stage (optimal) design as previously described, and is based on the proportion of evaluable subjects in the FAS who achieve CB at 24 weeks. At least 3/18 evaluable subjects must achieve CB in order for the arm to proceed to the second stage. If an arm proceeds to the second stage, ≥ 9/44 subjects must have CB at 24 weeks to deem the efficacy criteria to have been met in that arm. This is the minimum number of successes needed to rule out an unacceptably low, 10%, CB rate (lower limit of the 95% confidence interval). The exact 95% confidence intervals about the CBR at week 24 will be constructed.

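### If an arm ends with more than 44 evaluable subjects, does the 9/44 success rule leave the decision open?

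*Combined protocol and SAP*

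**What the plan says.** An evaluable subject is one who is treated and has centrally confirmed androgen receptor positive (AR+) status. Section 11.4.1 sets no ceiling on their number: "Subjects in the FAS who have centrally confirmed AR+ status; these subjects are the subjects in the primary efficacy analysis".

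Stage 1 is tied to identified subjects. An arm continues if "at least 3 subjects among the first 18 evaluable subjects randomized achieve CB" (Section 11.2). For stage 2, Section 4 says "the arm will proceed to the second stage of recruitment up to a total of 44 evaluable subjects per arm", and success is at least 9/44 (Sections 4, 11.2 and 11.4.3.2).

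Two further sentences bear on the point:

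- Section 11.2: "If at any time, 9 evaluable subjects in an arm achieve CB at week 24, the efficacy criteria for that arm has been met" (the sentence continues: "however, the arm should proceed to full accrual of 44 evaluable subjects in the successful arm(s").
- Section 11.4.3.2: the primary analysis "is based on the proportion of evaluable subjects in the FAS who achieve CB at 24 weeks", under the Simon rules and with the 9/44 criterion.

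Confirmed AR status is not an entry criterion. Inclusion criterion 4 asks for tissue to be available, for example "a minimum of 10 and up to 20 slides of archived tumor tissue for central laboratory confirmation of AR status and molecular subtyping". Subjects who are not confirmed are replaced "in order to accrue the 44 subjects of the evaluable subset of the FAS" (Protocol Summary, over-enrollment paragraph).

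**The concern.** A cut-off of 9 is calibrated to 44 subjects. A subject can be randomized and dosed and only later be found evaluable or not, so an arm might finish with 45 or 46 evaluable subjects instead of 44. Section 11.4.1 would put all of them in the primary analysis.

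Two readings then seem possible. On a count reading, the first clause of the Section 11.2 sentence is taken alone and 9 CBs are enough whatever the denominator. On a proportion reading, the observed rate must reach 9/44 = 20.5%, which takes 10 CBs at 45 to 48 subjects.

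Suppose an arm has 8 CBs in its first 44 evaluable subjects and one more among subjects 45 and 46. By count it succeeds with 9. By proportion it fails, since 9/46 = 19.6%. On the first 44 it fails with 8. At stake is an arm's go/no-go result. In an open-label trial, a choice among these readings made after the data are seen would be open to criticism.

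**Working it through.** **Inputs** (Sections 11.1 and 11.2): null rate 0.10, alternative 0.30, one-sided alpha 0.025, power 90%, 18 subjects in stage 1 with at least 3 CBs to continue, 44 in total with at least 9 CBs for success.

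**Formula.** With final size N, cut-off c and true rate p, the probability of declaring success is

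R(N, c, p) = sum over x = 3 to 18 of P[Bin(18, p) = x] × P[Bin(N − 18, p) ≥ c − x].

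**The plan's own design.** R(44, 9, 0.10) = 0.0236 and R(44, 9, 0.30) = 0.904, so both stated error rates are met. A full search for the Simon optimal design under these inputs returns the same design: stop at 2 or fewer in 18, fail at 8 or fewer in 44.

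**If an arm overran.** The document gives no turnaround time for central AR testing, so N = 45 to 48 is an assumed range for illustration. The proportion cut-off is the smallest whole number not below 9N/44, which is 10 throughout this range (9 × 45/44 = 9.2; 9 × 48/44 = 9.8).

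| N | 9 CBs: alpha | 9 CBs: power | 10 CBs: alpha | 10 CBs: power |
|---|---|---|---|---|
| 44 (planned) | 0.0236 | 0.904 | – | – |
| 45 | 0.0265 | 0.911 | 0.0106 | 0.874 |
| 46 | 0.0296 | 0.916 | 0.0122 | 0.885 |
| 47 | 0.0329 | 0.921 | 0.0140 | 0.894 |
| 48 | 0.0363 | 0.925 | 0.0159 | 0.902 |

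So the count reading exceeds 0.025 from N = 45, by 0.0265 − 0.025 = 0.0015 there. The proportion reading is conservative and has power below 90% at N = 45 to 47.

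**How often a decision would change.** The natural reference is the first 44 evaluable subjects. Nine CBs in the first 44 imply at least nine in any larger set, so the two rules disagree with probability R(N, 9, p) − R(44, 9, p):

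| True CB rate | R(44, 9) | R(45, 9) | R(46, 9) | Changed at N = 45 | Changed at N = 46 |
|---|---|---|---|---|---|
| 10% | 0.0236 | 0.0265 | 0.0296 | 0.003 | 0.006 |
| 20% | 0.4746 | 0.4960 | 0.5162 | 0.021 | 0.042 |
| 30% | 0.9041 | 0.9108 | 0.9163 | 0.007 | 0.012 |

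Setting count against proportion at N = 46 gives larger figures (0.017, 0.114 and 0.031). The scaled cut-off of 10 is not in the protocol, however, so those figures compare two constructions.

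**What the text supports.** Section 4 and the Protocol Summary end recruitment at 44 evaluable subjects per arm. The Protocol Summary range of 36 to 88 evaluable subjects is 2 × 18 to 2 × 44, which leaves no room for a 45th. The Section 11.2 sentence about 9 CBs at any time goes on to say that accrual continues to 44, so it describes reaching the criterion early, on the way to 44. In Section 11.4.3.2, the word proportion describes the endpoint, and the rule beside it is 9 in 44.

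**The case for a change.** The strongest case for a change is that 44 is a recruitment target and not an analysis rule, and that nothing guarantees an arm stops there. Randomization is 1:1, the two arms may lose different numbers to unconfirmed AR status, and no section closes one arm at 44 while the other still recruits. The enrollment pause in Section 4 covers stage 1 only. If all 118 subjects were randomized, 59 per arm, and each were evaluable independently with probability 0.75, an arm would pass 44 with probability 0.48. One sentence would remove the doubt at no cost.

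Part of this stands. The text names the first 18 and does not name the first 44, and it has no rule for an arm that overruns. The 0.48, however, assumes that every replacement slot is used whether or not it is needed. The protocol brings in replacements only to reach 44, and 118 is an upper bound. The schedule of events and Section 7.1 also place AR status among the screening procedures. This makes a backlog of unresolved subjects at the 44th less likely, although the replacement rule shows that some may be randomized before confirmation.

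Section 11 calls itself an overview and leaves detail to a separate SAP, which is not in the text reviewed here. The decision set after accidental over-accrual is ordinary SAP detail. One cannot assume that the choice would be left until results are known.

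**Conclusion.** The concern does not call for a change. Followed as written, the plan recruits to 44 evaluable subjects per arm, applies 9/44, and has alpha 0.0236 and power 0.904. The sections do not contradict one another. The claim that the text supports two different decisions depends on reading half of a sentence in Section 11.2 and on a scaled cut-off that appears nowhere in the protocol.

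What remains is an unwritten rule for an event that is not planned. An analyst facing it would take the first 44 evaluable subjects in order of randomization, as stage 1 does with the first 18, and use any later subjects for estimation only. Should someone instead count 9 CBs in everyone, the excess over 0.025 would be 0.0015 at 45 subjects and 0.0046 at 46 (0.0296 − 0.025), in a phase 2 screening trial that makes no formal comparison between arms.

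This conclusion rests on accrual being managed to 44 as stated, and on any overrun being small. The document gives no figure from which its likelihood or size could be derived. The count-reading error does grow with N, reaching 0.0363 at 48, so a larger overrun would make the choice of decision set matter more.
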